2.3 Secondary Objectives

The mechanistic studies under this section are to document any systemic effects from the chitosan treatment, related magnitude and timing of AGE depletion to chitosan effects, and determine if chitosan can reduce tissue, as well as serum, AGE levels.

- Identify systemic effects of chitosan on redox status (RedoxSys, serum oxidized glutathione), inflammation (plasma cytokines, Toll-like receptor signaling), and insulin resistance (HOMA-IR).
- Determine if chitosan modifies bowel permeability (plasma endotoxin) and microbiome diversity (16s rDNA sequencing).
- Correlate changes in serum AGE levels (pan-AGE, carboxymethyllysine, methylglyoxal, pentosidine adducts) with changes in tissue AGE levels as determined by skin autofluorescence.
- Define the frequency of a $\geq 30\%$ reduction in total AGE levels from the pretreatment level. A frequency of 50% will be considered “interesting” for further study.

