Once the MTD is established, 27 additional subjects will be recruited at that dose level to better define toxicity and changes in AGEs. The maximum number of patients that can be accrued is 54. The primary measure of change in AGE is defined as a binary indicator of a 30% or greater decrease in plasma total AGE level between baseline and day 85 specimens. The proportion of patients with a 30% or greater decrease will be calculated with its exact 95% confidence interval. An exact binomial test will be based on a null hypothesized true proportion of 0.25 (i.e., 25% of patients have a $\geq 30\%$ reduction in AGE levels) which is too low to be of further interest. With an alternative of 0.50 and 33 patients, assuming a 1-sided alpha of 0.05, the power is 0.88. Graphical displays will be made to demonstrate patterns in AGE between baseline and day 85. The following analyses will be performed, and then data will be stratified by race, and analyses repeated to evaluate differences by race. Summary statistics (mean change between timepoints, standard deviations, medians) will be reported. Scatterplots and paired t-tests will be used to compare the mean change between baseline and day 85 with a 2-sided alpha of 0.05 for changes in AGE levels and changes in other variables of interest (e.g. race, BMI). Linear regression will be used to evaluate associations between continuous variables and changes in AGE levels with changes in AGE levels as the outcome. Transformations will be taken as appropriate and residual plots will be examined to evaluate assumptions of linear regression model. The investigators will add baseline levels of clinical parameters in the linear regression model to account for starting levels. Regression coefficients will be evaluated in terms of clinical effect size and statistical significance. Model results will be reported with 95% confidence intervals.

REFERENCES

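### Section 10.2 gives a power of 0.88 for the AGE response test, but the exact binomial test with the inputs printed there has power 0.92.

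*Combined protocol and SAP*

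**What the plan says.** The design of the AGE response analysis is in section 10.2. The endpoint is binary: whether a patient's plasma total AGE level drops by 30% or more from baseline to day 85. The test is named and its null value given: "An exact binomial test will be based on a null hypothesized true proportion of 0.25", a rate the plan regards as too low to pursue. The power statement follows: "With an alternative of 0.50 and 33 patients, assuming a 1-sided alpha of 0.05, the power is 0.88".

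The alternative of 0.50 agrees with section 2.3, which lists the frequency of a 30% or greater "reduction in total AGE levels from the pretreatment level" as a secondary objective and says "A frequency of 50% will be considered" interesting for further study. The 33 patients are consistent with the statement in section 10.2 that "27 additional subjects will be recruited at that dose level", added to six already treated at the MTD (27 + 6 = 33).

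Section 10.2 gives no rejection cut-off, no allowance for missing day-85 samples, and no indication that the power was approximated.

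**The concern.** An exact binomial test is fully determined by its null rate, sample size and alpha, and its power by adding the alternative. Section 10.2 prints all four, so a reader should be able to recover 0.88, and cannot.

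This is the only power statement in section 10, and it supports the sample size used for the AGE response. A mismatch leaves two possibilities: the number is wrong, or the number belongs to inputs other than those printed. The second would affect how a borderline result is read. At 33 patients the exact rule is at least 13 responders at one-sided 0.05 but at least 14 at one-sided 0.025, so 13 of 33 would be positive under one and negative under the other.

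**Working it through.** **Inputs, all from section 10.2:** exact binomial test; null rate 0.25; alternative 0.50; n = 33; one-sided alpha 0.05; stated power 0.88.

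**Formulas.** For a rule that rejects when X ≥ r:

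- attained alpha(r) = Σ from x = r to 33 of C(33, x) · 0.25^x · 0.75^(33−x)
- power(r) = Σ from x = r to 33 of C(33, x) · 0.50^33

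The test uses the smallest r with attained alpha no greater than 0.05.

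**Step 1: try to reproduce 0.88 with the stated test.**

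| Reject if responders ≥ | Attained alpha (rate 0.25) | Power (rate 0.50) |
|---|---|---|
| 12 | 0.0987 | 0.9599 |
| 13 | 0.0484 | 0.9186 |
| 14 | 0.0213 | 0.8519 |
| 15 | 0.0084 | 0.7566 |

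A cut-off of 12 exceeds 0.05, so the rule is at least 13 of 33. Power is 0.919, and 0.919 − 0.88 = 0.039. The stated figure is not reproduced.

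**Step 2: could another cut-off give it?** No. Between cut-offs 13 and 14 the power drops in one step from 0.919 to 0.852, passing over 0.88. Requiring the lower limit of the exact two-sided 95% interval to exceed 0.25 gives the cut-off of 14 and power 0.852. The mid-p version keeps the cut-off at 13.

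**Step 3: could an approximation give it?** The usual normal approximation, with the null variance for the critical value and the alternative variance for power, is

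Φ{[(0.50 − 0.25)·√33 − z·√(0.25·0.75)] / √(0.50·0.50)}.

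- One-sided 0.05 (z = 1.645): Φ[(1.436 − 0.712)/0.5] = Φ(1.448) = 0.926.
- One-sided 0.025 (z = 1.960): Φ[(1.436 − 0.849)/0.5] = Φ(1.175) = 0.880.

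Other approximations at n = 33 and one-sided 0.05 give 0.890 (alternative variance only), 0.899 (two variances with continuity correction) and 0.914 (arcsine). Across the forms tried, the range is 0.854 to 0.953.

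**Step 4: which changed inputs round to 0.88?**

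| Method | n | One-sided alpha | Power |
|---|---|---|---|
| Two-variance normal | 33 | 0.025 | 0.880 |
| Two-variance normal | 27 | 0.05 | 0.880 |
| Exact (at least 15) | 36 | 0.025 | 0.879 |

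Each departs from the printed design in at least one respect. Since several fit, none can be named as the source.

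**Step 5: dependence on the number analysed.** The dose-level table in section 10.1 shows an expansion of +30 at level 4, which gives 36 patients with six already treated, or 33 with three. At 36 and one-sided 0.05 the rule is at least 14, attained alpha 0.046, power 0.934. The plan gives no dropout rate. As an assumption, if one, two or three of 33 lack a day-85 value, the cut-off stays at 13 and power is 0.892 (n = 32), 0.859 (n = 31) or 0.819 (n = 30).

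**The case against.** The best defence is that the plan calls the test exact but does not say that the power was computed exactly, so 0.88 may be an unlabelled normal approximation. This explains little. None of the approximations tried at the printed n and alpha gives 0.88, and the one that gives 0.880 at 33 patients needs one-sided 0.025. An approximate power quoted for an exact test should in any case be labelled.

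A second objection is that little rests on the figure. The primary objective is the MTD, the response rate is secondary, and no sample size or stopping rule changes. That is accepted and sets the severity.

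A third objection has more force. Calling the error conservative assumes that the printed inputs are the intended ones. Section 10.2 also plans an exact 95% interval and uses two-sided 0.05 for its t-tests, so one-sided 0.025 is a plausible intention. In that case the exact power at 33 is 0.852, 0.88 is too high rather than too low, and the cut-off moves to 14. The correction should therefore start with confirmation of the inputs.

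**Conclusion.** The stated power is wrong for the stated test. From the inputs in section 10.2 the exact power is 0.919, which rounds to 0.92, with rejection at 13 or more of 33 and attained one-sided alpha 0.048. The discrepancy is 3.9 percentage points.

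This assumes that all 33 patients have both baseline and day-85 values and that "assuming a 1-sided alpha of 0.05" is meant literally. On that reading the error understates power, 33 patients remain sufficient, and the planned analysis is unaffected. The point is minor, and confidence in the arithmetic is high. What produced 0.88 cannot be determined from the documents.

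**What to change.** Confirm that the null of 0.25, alternative of 0.50, 33 patients and one-sided 0.05 are the intended inputs. If they are, change 0.88 to 0.92 in section 10.2. It would help, though it is not essential, to add the rule: the null is rejected when at least 13 of 33 patients respond, with attained one-sided alpha 0.048 and power 0.92 at a true rate of 0.50.

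If other inputs were meant, print those with their exact power; for example, one-sided 0.025 with 33 patients means at least 14 responders and power 0.85. Recompute if reconciling the 27 additional subjects in section 10.2 with the +30 in the section 10.1 table changes the number analysed.

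If the printed inputs stand, the cost is one corrected number, with no extra patients and no change to the analysis. If a different alpha was intended, the stated alpha and the implied cut-off change too, which is still a text amendment.

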Chitosan has been extensively tested in human for indications related to obesity, glucose control, hypertension, renal failure, and the metabolic syndrome. Table 1 is a partial selection of trials that can be found in the published literature. These studies include 371 patients treated with oral chitosan, in doses up to 5,250mg daily, and for periods of up to 1 year. These doses include the range of proposed dosing in our study. A variety of benefits were claimed. No study reported SAEs or significant (grade 3,4) AEs. When reported, compliance was generally high, and in randomized studies, was similar between the chitosan and placebo arms. Described AEs

predominately included GI complaints (constipation, bloating, full feeling, gas) but these were also described in the placebo arms. Where attribution was made, constipation was described as “not related” to the study drug. Three studies made no comment on chitosan toxicity. While the toxicity in these studies may be unclear, it is unlikely that the chitosan intervention was highly toxic. (58,62-72)

Table 1. Toxicity of Chitosan in Humans

disease	study type	chitosan	placebo	chitosan dose	duration	effects	toxicity	ref
renal Dz on dialysis	randomized	40	40	1350mg/d vs placebo	12 wks	lower creatinine, cholesterol; improved Hb, wt	"no clinically problematic symptoms"	1
elderly	single arm	18	18	5100mg/d	8 wks	immune cytokine increase	"no safety problems"	2
high cholesterol	crossover	65	65	2400mg/d vs placebo	3 months	no reduced chol, ApoE	no SAEs. Reported AEs were mild (GI complaints, pains, swelling, rash, heart palpitation, insomnia). 7/65 (chito) vs 5/65 (placebo) dropouts	3
high cholesterol women	randomized	46	44	1200mg/d vs placebo	56 days	lowered chol	few; no SAE; 4/46 AE in chitosan (thirst x 3, aphthous ulcer x 1), 2/44 AE in placebo (abd fullness, HA)	4
healthy males	single arm	7		5,250mg/d	12 days	no reduced fat absorption	no comment	5
healthy adult	randomized (chitosan vs orlistat)	6	6	2670mg/d	21 days	no increase in fat excretion	"well-tolerated, with no subjects reporting SAEs or discontinuing study. Majority of AEs were gastrointestinal in nature, reported by 8% of subjects on chitosan"	6
adult	randomized	44	44	1000mg/d vs placebo	112 days	no reduced wt or body fat	72.3% completed study	7

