APPENDIX A. SCHEDULE OF PROCEDURES AND ASSESSMENTS

Study Activity	Screen ^c	Day 1 ^c	Day 14 ^g	Day 29	Day 57 ^g	Day 85/ End of study ^{a, d}	Specimen	
Demographics	X							
Full Physical Exam,	X							
Focused Physical Exam,		X				X		
Medical History to include: 
 • Duration of ADT • Extent of cancer • Personal history of diabetes mellitus • Current medications 	X	X						
Interim Medical History		X				X		
Anthropometric Measurements (height, weight)	X	X				X		
CBCD	X	X				X		
CMP (fasting) ^g	X	X				X		
Phosphorus	X	X				X		
PSA	X	X				X		
Assessment of toxicity		X	X ^g	X ^g	X ^g	X		
testosterone	X	X				X		
Chitosan			X-----X					
Drug diary review ^e						X		
Informed consent	X							
Insulin Resistance (HOMA-IR)		X ^f				X	Plasma ^b	
CRP, AGE species and precursors		X ^f				X	Serum ^b	
RedOx status (ORP, reduced glutathione)		X ^f				X	Plasma ^b	
RAGE, TLR expression, signaling		X ^f				X	Whole blood ^b	
Microbiome profiling		X ^f				X	Stool	
AGE species		X ^f				X	Urine ⁱ	
Tissue AGE level by autofluorescence		X				X		
Food Recall Dietary AGE content ^h		X ^f				X		
QOL (FACT-P and AUA)		X ^f				X		

- All days are +/- 5 days
- 2x7mL EDTA blood (=plasma), 2x7mL clot tube (=serum), 1x7mL sodium heparin tube (=whole blood).
- Screening assessments to be done within 28 days of registration. Screening assessments may be used for the day 1 assessments if they were completed within 28 days of day 1. The CMP used for eligibility confirmation does not have to be fasting, but a fasting CMP will need to be collected prior to day 1 drug administration. Fasting is defined as nothing containing calories since the previous midnight.
- If the subject goes off study less than 2 weeks after start of dosing, "end of study" labs and questionnaires will not be done.
- The drug diary will be given to each subject for completion during the study.
- Research procedures (excluding informed consent) may be done at any point after informed consent and prior to first dose of drug (on day 1). Research blood, urine and stool samples will be taken to the participating research lab(s) for processing.

NCT # NCT03712371

CTO # 102928

Version Date: 09/09/2020

- g) On day 14, day 29, and day 57 (+/- 5 days), compliance and adverse events will be assessed via phone using the phone contact guide in appendix D.
- h) Food recall using the NCI quick food scan and the NIH's "Eating at America's Table Study" Quick food scan.

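### Section 10.2's power of 0.88 for 33 patients is not what its exact test gives (0.92 with complete data), and it has no attrition allowance or missing-specimen rule

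*Combined protocol and SAP*

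**What the plan says.** Section 10.2 defines response as a fall of 30% or more in total AGE between the baseline and day-85 specimens. On the test it says: "An exact binomial test will be based on a null hypothesized true proportion of 0.25". The power statement is: "With an alternative of 0.50 and 33 patients, assuming a 1-sided alpha of 0.05, the power is 0.88".

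The same section recruits 27 further subjects once the MTD is set. With 6 already treated at that dose, this makes 33. Table 3 in section 10.1 instead shows +30 at the top dose level, and the stated maximum accrual of 54 equals 4 × 6 + 30.

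Several provisions bear on whether a day-85 specimen exists:

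- Section 4.4 lists reasons to discontinue, including a change in anti-cancer therapy, procedures under general anesthesia and unresolved toxicity.
- Section 7.4 stops specimen collection once a subject withdraws or is withdrawn.
- Appendix A footnote d cancels end-of-study labs and questionnaires "If the subject goes off study less than 2 weeks after start of dosing".
- The last visit column in Appendix A covers both day 85 and end of study, so a patient leaving after week 2 may give an earlier specimen.

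Section 10 contains no attrition allowance, replacement rule, analysis set or rule for a missing or early specimen.

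Table 1 (section 1.6.4) reports losses in three earlier chitosan studies: "7/65 (chito) vs 5/65 (placebo) dropouts" over 3 months; "72.3% completed study" over 112 days, with no arm named; and 2 of 15 withdrawn on chitosan over 28 days.

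**The concern.** The power calculation uses the same 33 patients who are expected to be treated at the MTD, so it treats every one of them as evaluable. The plan does not say what happens to a patient without a day-85 specimen, or to one whose only post-baseline specimen was taken early. Two things are at stake. The first is the power figure, which should match the stated test and show how it behaves under loss. The second is the test result itself. If the denominator is not fixed in advance, it could be chosen after the data are seen, and for some results that choice decides whether the null is rejected.

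**Working it through.** **Inputs (section 10.2).** Null proportion 0.25; alternative 0.50; one-sided alpha 0.05; n = 33; exact binomial test; stated power 0.88.

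**Step 1. Reproduce the stated power.** The cut-off r is the smallest value with P(X ≥ r | n, 0.25) ≤ 0.05. Power is P(X ≥ r | n, 0.50). At n = 33:

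- r = 12: alpha 0.0987, too large.
- r = 13: alpha 0.0484, power 0.9186.

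The stated test therefore has power 0.92, not 0.88. A normal approximation gives

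Φ{[√n(0.50 − 0.25) − z√(0.25 × 0.75)] / √(0.50 × 0.50)}.

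This is 0.880 with n = 33 and two-sided alpha 0.05 (z = 1.96), and also 0.880 with n = 27 and one-sided alpha 0.05 (z = 1.645). Either could be the source of 0.88, and the documents do not say. Neither is the stated test on 33 patients.

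**Step 2. Power by number evaluable (exact, cut-off redrawn at each n).** 33: 0.919. 32: 0.892. 31: 0.860. 30: 0.819. 29: 0.868. 28: 0.828. 24: 0.729. The path is uneven because the cut-off is a whole number.

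**Step 3. Power under assumed loss.** Let d be the probability of no usable specimen. Take 0.50 as the response rate among patients with a specimen.

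- Completers only: average the exact power over m ~ Binomial(33, 1 − d), redrawing the cut-off for each m.
- Missing as non-response: P(X ≥ 13 | 33, 0.50(1 − d)). For d = 7/65 the response probability is 0.50 × 0.892 = 0.446.

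| Assumed loss d | Source | Completers only | Missing as non-response |
|---|---|---|---|
| 0% | none | 0.919 | 0.919 |
| 3% | illustration | 0.891 | 0.889 |
| 4% | illustration | 0.882 | 0.878 |
| 5% | illustration | 0.875 | 0.866 |
| 10.8% | 7/65, Table 1 | 0.843 | 0.781 |
| 13.3% | 2/15, Table 1 | 0.832 | 0.734 |
| 27.7% | 100% − 72.3%, Table 1 | 0.765 | 0.412 |

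Power stays at about 0.88 up to roughly 4% loss under either rule.

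**Step 4. Effect of the expansion size.** If Table 3's +30 is added to 6, then 36 are treated at the MTD (r = 14, alpha 0.0461, power 0.934 with no loss). At 10.8%, 13.3% and 27.7% loss, power is 0.882, 0.869 and 0.798 on completers, and 0.804, 0.759 and 0.427 with missing as non-response.

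**Step 5. Why the denominator must be fixed.** Suppose there are 12 responders and 4 missing specimens. On completers, 12/29 gives P(X ≥ 12 | 29, 0.25) = 0.039, which rejects. On all treated, 12/33 gives 0.099, which does not. Nothing in section 10.2 says which applies.

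**The case against.** A reader might infer that 0.88 requires a specimen from all 33 patients, that the exit rules make this impossible, and that the stated power is therefore not delivered. The documents do not support that, for these reasons:

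- **Not all 33 are needed.** With 32 evaluable the exact power is 0.892. The stated 0.88 is about 4 points below the exact value, so it already absorbs a small loss.
- **The exit rules carry no rates.** They make loss possible, not certain. Footnote d cancels the final labs only for exits under 2 weeks, so later leavers may still give a specimen.
- **The Table 1 rates are borrowed.** They come from 3 of 12 rows, in people with high cholesterol, general adults and overweight adults, not men on ADT. The 72.3% completion names no arm, and it produces the 0.41. Another row reports no discontinuations.
- **The expansion size is unclear.** With 36 at the MTD, completers-only power is still 0.88 at 10.8% loss.
- **The meaning of 0.50 matters.** If it is the response rate among all treated patients with missing already counted as failure, power on 33 is 0.92 whatever the loss.

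A reader might also infer that a completers-only analysis must inflate the response rate because leavers are intolerant. The cited dropouts are nearly equal on placebo (7/65 vs 5/65; 2/15 vs 2/15), and no document gives response by completion status. That bias is possible but not shown.

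All these limits stand. They leave untouched the mismatch between 0.88 and the stated test, and the lack of any rule for missing or early specimens. Section 10.2 does specify day-85 specimens, which suggests that early ones do not count, but it does not say whether such patients then leave the denominator or count as non-responders.

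**Conclusion.** The point holds in a limited form. On its own inputs the test has power 0.92 with complete data, so 0.88 is wrong as written, in the conservative direction. The 33 makes no allowance for loss, and the denominator is not defined. Power with 33 treated falls below 0.88 once loss exceeds about 4%. At loss rates like those in Table 1 it would be 0.84 to 0.76 on completers, or 0.78 to 0.41 with missing as non-response. Those ranges assume that the Table 1 losses carry over to this population, that each lost patient has no usable specimen, that loss is independent between patients, and that 0.50 applies to patients with a specimen. They show sensitivity and do not predict this trial's power.

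The AGE response is a secondary objective; the primary objective, the MTD, is unaffected. The correction is still worth making, because the missing-specimen rule can change the result of the test.

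**What to change.** Amend section 10.2 as follows:

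1. Define the primary analysis set as all patients who start chitosan at the MTD.
2. Count a missing specimen, or one taken before the day-85 window, as non-response. State the window, since section 5.1 gives ±3 days and Appendix A gives ±5 days; these need reconciling.
3. Give completers, with and without early specimens, as sensitivity analyses.
4. Restate the power for 33 patients as 0.92 with no loss (reject at 13 or more, alpha 0.048), plus a range over assumed loss rates. Say whether 0.50 applies to all treated patients or to completers.
5. Reconcile the expansion size (27 in the text, +30 in Table 3) and the maximum of 54, and base the restated power on the resulting number.

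The cost is a few sentences and possibly a less favourable stated power under loss. No extra patients or procedures are needed.

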The receptor for AGEs, RAGE, is also overexpressed in a number of tumors and evidence suggests a direct link between RAGE activation with the proliferation, survival, migration, and invasion of tumor cells. Loss of RAGE in inflammatory mouse models confers resistance to skin carcinogenesis and suppresses tumor growth (19). In prostate cancer, RAGE preferentially interacts with AGE over other potential RAGE ligands and AGE treatment of prostate cancer cells induces both cell growth and invasion (26).

Our group examined circulating and tumor AGE levels in clinical specimens of prostate cancer and identified a race specific, tumor-dependent pattern of accumulation (4). AGE levels were significantly elevated in both serum and tumor, with highest accumulation occurring in more aggressive tumors. When examined in a matched cohort of patients, high AGE levels in the serum correlated with high AGE accumulation in cancer tissue (4). Significantly, when the data were stratified by race, AGE metabolite levels were significantly higher in serum from African American cancer patients compared with Caucasian. These initial data indicate that AGEs may represent a potential mechanistic link between cell metabolism and cancer, which may also provide a biologic consequence of the lifestyle risk factors that drive cancer health disparity.

Based on associations between active metabolism, lifestyle, and immune response, increases in exogenous AGE accumulation may represent a biologic mechanism contributing to cancer disparity and may represent a novel paradigm to explaining the increased cancer incidence and mortality figures observed within minority populations. A series of recent articles has highlighted the tumor-associated immune response as a critical pathway contributing to cancer disparity in

African Americans. An examination of expression differences based upon tumor composition shows that cytokine signaling associated with an increased immune response was found to be a predominant pathway increased in African American prostate cancer patients (2). Upon closer analysis, the majority of race-specific differential gene expression was found in the stromal compartment of the tumor (2). A similar race-specific increase in immune response gene copy number and gene expression was seen in matched radical prostatectomy tissues (27) and in Gleason 6 prostate tumors (1).

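### Section 10.2 aims to evaluate differences by race, but its analyses describe one race at a time and name no between-race contrast or interval

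*Combined protocol and SAP*

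**What the plan says.** Section 10.2 first defines the main AGE measure, "defined as a binary indicator of a 30% or greater decrease in plasma total AGE level" between baseline and day 85, and gives its pooled exact binomial test in 33 patients. The race instruction comes next: "The following analyses will be performed, and then data will be stratified by race, and analyses repeated to evaluate differences by race".

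The analyses after that sentence are:

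- Descriptive: "Summary statistics (mean change between timepoints, standard deviations, medians) will be reported".
- Tests: "Scatterplots and paired t-tests will be used to compare the mean change between baseline and day 85", at a two-sided alpha of 0.05, applied to "changes in AGE levels and changes in other variables of interest (e.g. race, BMI").
- Regression: "Linear regression will be used to evaluate associations between continuous variables and changes in AGE levels", with AGE change as the outcome. Covariates: "The investigators will add baseline levels of clinical parameters in the linear regression model to account for starting levels". Model results carry 95% confidence intervals. Transformations are left to judgement, in the sentence on regression assumptions.

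Section 10.2 does not say which race groups form the strata. Section 1.4 compares African American and Caucasian patients as background, and Appendix A lists only demographics at screening. The objectives in Sections 2.2 and 2.3 contain no race comparison.

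**The concern.** The stated purpose is a comparison, and the listed methods do not make one. A paired t-test within a race asks whether that race's mean changed from baseline. A regression fitted within a race cannot estimate a race effect, and the pooled regression is described for continuous predictors, which race is not. The only other mention of race is in the paired t-test examples, where it cannot be carried out because a patient's race is the same at both visits.

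The results section would therefore hold a set of p-values for each race and nothing that sets the races against each other. Race is a main theme of the rationale in Section 1, so readers will look for this result. With small and possibly unequal strata, one race can easily be significant and the other not when the true effect is identical.

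Scale is also open. The main AGE measure is proportional, while the reported summary is a mean change whose scale is not fixed. Section 1.4 reports that "AGE metabolite levels were significantly higher in serum from African American cancer patients compared with Caucasian". If baselines differ, an absolute change can differ between races even when the percentage reduction is the same.

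**Working it through.** **Plan's own figure.** The plan gives no figure for any race comparison. Its one power figure, 0.88, is for the pooled binomial test and is not used here. (The stated exact test with n = 33 needs 13 or more responders; its size is 0.048 and its power 0.919, so 0.88 is conservative. That is a separate matter.)

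**Does each listed analysis contrast the races?**

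| Analysis in Section 10.2 | What it estimates within a race | Between-race contrast? |
|---|---|---|
| Mean change, SD, median | that race's change | no; a reader could derive one |
| Paired t-test | whether that race's mean change is zero | no |
| Regression on continuous variables | slopes within that race | no |
| Paired t-test of change in race | nothing; race is constant | no |

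**How often within-race tests disagree when there is no race difference.**

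From the plan: 33 patients, paired t-test, two-sided alpha 0.05. Assumed, because the documents give no split or SD: two race groups of 16/17, 11/22 or 8/25, all patients evaluable, normal changes, and the same true mean change d (in SD units) in both.

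Power in a stratum of size n: P(n, d) = Pr(|T| > t(0.975, n-1)), where T is noncentral t with n-1 degrees of freedom and noncentrality d√n.

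Chance that exactly one stratum is significant: P1(1-P2) + P2(1-P1).

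| d | 16/17: P1, P2, result | 11/22: P1, P2, result | 8/25: P1, P2, result |
|---|---|---|---|
| 0.3 | 0.203, 0.214, **0.330** | 0.147, 0.269, **0.337** | 0.114, 0.302, **0.347** |
| 0.5 | 0.465, 0.491, **0.499** | 0.323, 0.609, **0.539** | 0.232, 0.670, **0.591** |
| 1.2 | 0.994, 0.996, **0.010** | 0.947, 1.000, **0.053** | 0.828, 1.000, **0.172** |

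Example, 11/22 at d = 0.5: 0.323 × 0.391 + 0.609 × 0.677 = 0.126 + 0.412 = 0.539 after rounding. Under the same assumptions and equal SDs, a direct two-sample t-test rejects in 5% of trials.

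**Scale.** If the baseline means are B1 and B2 and each race falls by 30%, the mean absolute changes are 0.3·B1 and 0.3·B2. They differ by 0.3(B1-B2), which is not zero unless the baselines agree. The mean log changes do not carry this difference. The documents do not give B1-B2, so no size is attached.

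**What a direct contrast would deliver.**

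- Difference in mean log change: the 95% half-width is t(0.975, 31) × √(1/n1 + 1/n2) = 2.040 × 0.348, 0.369 or 0.406 = 0.71, 0.75 or 0.83 SD.
- Difference detectable with 80% power (noncentral t, 31 degrees of freedom): 1.01, 1.07 or 1.18 SD.
- Difference in responder proportion (expected Newcombe half-width): 0.301, 0.311 or 0.328 if 50% respond in both races; 0.277, 0.288 or 0.307 if 25% respond. These are the plan's alternative and null rates.

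**The case against.** The strongest reply is that nothing in the plan is invalid. Race is in no objective and carries no alpha or power claim. Means and SDs by race are reported, so a reader can form a difference. Section 10.2 also asks for coefficients to be judged on clinical effect size and reported with intervals, which is not a habit of reading p-values alone. All of this stands, and it is why the point is minor. It does not supply the missing contrast: those intervals belong to continuous predictors, and a difference that readers must build themselves has no agreed scale or groups.

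Three stronger readings are tempting, and the documents do not support them.

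- A reader might infer that a race difference will be declared when one race is significant and the other is not. The plan does not say so. The percentages above show how unreliable that inference would be; they are not an error rate of the plan.
- A reader might infer that the responder proportion is left out of the race analysis, because the race sentence follows it. That is one literal reading, and the text is unclear.
- A reader might infer that the planned mean change is absolute and would produce a false race difference at some known rate. The plan does not fix the scale. Section 1.4 gives no size for the baseline gap, and it concerns serum, whereas Section 10.2 names plasma. Only the possibility can be stated.

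The reply that a contrast in 33 patients will be imprecise is also correct. It argues for showing the interval and not for omitting it.

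**Conclusion.** The point holds as a cheap improvement of minor weight. Section 10.2 states a purpose that its listed methods do not serve. It names no between-race contrast, interval, scale or groups, leaves the race breakdown of the responder measure unclear, and includes one instruction on race that cannot be carried out.

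The only inferential output by race is within-race. Under an equal true effect it would be discordant in roughly a third of trials at 0.3 SD and in half or more at 0.5 SD. At 1.2 SD it is rare with an even split and reaches 17% at 8/25. These figures rest on the assumed splits, two groups, normal changes and full evaluability. The gap in specification does not depend on them. The MTD and the pooled AGE test are unaffected.

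**What to change.** In the sentence containing "The following analyses will be performed, and then data will be stratified by race, and analyses repeated to evaluate differences by race", keep the stratification and replace what follows it with:

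> and analyses repeated by race as description only. Race differences are exploratory and will be estimated as the between-race difference in mean log (proportional) change in total AGE from baseline to day 85, and as the difference in the proportion with a 30% or greater decrease, each with a 95% CI, between race groups named in advance (for example African American and Caucasian).

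Delete race from the paired t-test examples.

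A baseline-adjusted regression with a race term is best left out. If the team wants it, the text should say that it answers a different question when the races start at different AGE levels, so a non-zero race term would not by itself show a different proportional reduction.

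The cost is wording and two exploratory estimates from data already scheduled in Appendix A. The downside is width: about 0.71-0.83 SD for the difference in mean log change and about 0.28-0.33 for the difference in proportions. The change gives an honest interval, and probably not a decisive answer.
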